## INTRODUCTION

Pilonidal cyst was first described by Hodges in 1880^1. The disease of pilonidal cyst is also known as “Jeep disease”, due to the fact that, during World War II (1941-1945), several American soldiers (about 80,000) suffered from this disease, because, either they were driving for long hours on uneven, destroyed by war, roads, or, they were spending time sitting at military vehicles like jeep, trucks and tankers, resulting in being submitted to surgical operation, in order to alleviate the arousing pilonidal cyst problem, at USA military hospitals.

Pilonidal cyst, is considered as one of the most common diseases of the subcutaneous tissues of the sacrococcygeal region. This situation is the result of hair penetrating into the skin, a situation not uncommon in this anatomical area. In a study including 50,000 college students, pilonidal cyst occurrence, in males, was 1.1%, which was 10 times higher compared to females, although a considerable rate of them was asymptomatic. Evidence from studies in England, also, indicate that the disease is more frequent in men than women (1 to 3). The disease is more common in Caucasians than in Asians or Africans due to the differences in their hair characteristics and the respective hair development pattern. Risk factors include the following: sedentary life (44%), positive family history (38%), obesity (50%) and regional irritation (34%). The disease usually presents during the age of 16–20 and prevalence is decreasing drastically after the 25th year of age. This disease rarely develops before the adolescence and after the 40th year of age.

Treatment usually depends on the condition of the disease. An acute abscess is usually controlled with incision and drainage. A chronic pilonidal cyst is best treated with a surgical procedure that involves complete resection of the cyst along with the coexisting fistulas, in order to ensure the minimum reoccurrence rate. There are two choices after surgical resection, secondary intention wound healing or primary trauma closure, with or without a flap. The surgical procedure can be performed with the administration of local anesthesia in the outpatient office or in a day-clinic, or with the use of general anesthesia depending on the condition of the patient.

Post operatively secondary intention wound healing is applied in many cases, especially when factors like infection, necrotic tissue or inflammatory tissue are

introduced. There are many dressings that can be used for the care of a surgical trauma. The ideal dressing used should have some special characteristics such as absorption of exudates without leakage, provision of a dry environment that prevents bacteria from entering the wound and facilitation of easy appliance, as well as removal. Choosing the right dressing is not based on a certain protocol, but mostly on the surgeon preference.

In the current study our objective is the comparison between different wound dressings and how they can affect secondary intention wound healing in patients that have been subjected to surgical resection of pilonidal cyst. Emphasis will be given at the postoperative quality of life of these patients.

## CHAPTER 2

### OBJECTIVE

The current study aims at comparing two groups of patients that will be subjected to surgical resection of pilonidal cyst and secondary intention wound healing. In the first group, dressings like alginate cord with silver and high G cellulose will be used for filling of the wound cavity and a hydrocapillary dressing for sealing and waterproofing the wound. In the other group, simple gauze dressings for the coverage of the wound cavity will be used. Comparison of the two groups will involve all the endpoints that indicate whether such dressings can facilitate faster wound healing, enabling, thus, patients to faster return to their everyday activities. Furthermore, a parameter that has not been, previously, studied, the quality of life after the surgical excision of the pilonidal cyst, by using the SF – 36 and the Quality of life with Chronic Wound questionnaire, will, also, be investigated.

# CHAPTER 3

## MATERIALS AND METHODS

### **1. Estimation of the necessary study sample size**

According to literature, the mean time required for wound healing of patients subjected to pilonidal cyst resection is  $60.4 \pm 6.2$  days. Therefore for a 5% decrease in the duration of the healing process and with an 1:1 enrollment ratio between the two groups, with alpha 0,05 and 90% power, the required number of patients in each group is 89. The total amount of patients required for completion of the study is 178. Patients that will not complete follow-up will be excluded and replaced by other patients.

### **2. Disease staging system**

Pilonidal cyst will be staged according to the following classification system.

Type I Pit(s) on the natal cleft

IA Asymptomatic one or more pit(s) on the natal cleft without a history of abscess

IB Symptomatic and / or more than one pit on the natal cleft

Type II Pit(s) on either side of the natal cleft

IIA Distance from the natal cleft  $< 2.5$  cm

IIB Distance from the natal cleft  $> 2.5$  cm

Type III Pits on both side of the natal cleft

Type IV Recurrent pilonidal disease

### **3. Inclusion Criteria**

- Male or female
- Pilonidal cyst
- Age: 18 to 80 years
- American Society of Anesthesiologists (ASA) score: I, II, III, IV
- Disease stage I,II,III and IV

### **4. Exclusion Criteria**

- Pilonidal abscess
- Patient age  $\geq 80$  years or  $< 18$  years

- Pilonidal abscess

## 5. Randomization

The randomization of the patients, between the two groups, will be performed using a software and a 1: 1 allocation ratio will be performed. Furthermore, an opaque envelope, which will contain the allocation group for the specific patient, will be opened preoperatively upon the entry of the patient into the surgical room.

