## 6. Blinding

Blinding will exist at the level of the investigator who will record the data postoperatively. There will be no blinding at the level of the surgeon or the patient.

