## 7. Endpoints

### *Primary Outcome Measure:*

- Wound healing time. Postoperative required time for wound healing. Measurement unit: days. [Time Frame: Maximum time frame 50 days postoperatively]

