### *Secondary Outcome Measures:*

- Postoperative return to everyday activities. Time required for returning to everyday activities. Measurement unit: days [Time Frame: Maximum time frame 50 days postoperatively]
- Postoperative pain level. Pain level after surgery, quantified with the use of the VAS scale. [Time Frame: 7, 14, 21, 28, 35, 42 and 49 days postoperatively]
- Postoperative analgesics consumption. Number of analgesic pills consumed per day after surgery. Measurement unit: pills per day [Time Frame: 7, 14, 21, 28, 35, 42 and 49 days postoperatively]
- Overall satisfaction level. Satisfaction level measured at a 0-10 scale [Time Frame: 50 days postoperatively]
- Cost of the material. Overall cost of the dressings applied [Time Frame: Maximum time frame 50 days postoperatively]
- Wound care visits. Number of required visits for postoperative wound care for each patient per week.[Time Frame: 7, 14, 21, 28, 35, 42 and 49 days postoperatively]
- Trauma secretions. Trauma secretions leading to extra dressing care. If such an episode occurs, then it will be defined as=1 'YES' If such an episode does not occur,

then it will be defined as=0 'NO' [Time Frame: 7, 14, 21, 28, 35, 42 and 49 days postoperatively]

- Wound contamination. Contamination of the wound trauma. If such an episode occurs, then it will be defined as=1 'YES' If such an episode does not occur, then it will be defined as=0 'NO' [Time Frame: Maximum time frame 50 days postoperatively]
- Wound erythema. Erythema of the wound. If such an episode occurs, then it will be defined as=1 'YES' If such an episode does not occur, then it will be defined as=0 'NO' [Time Frame: Maximum time frame 50 days postoperatively]
- Wound hematoma. Hematoma of the wound. If such an episode occurs, then it will be defined as=1 'YES' If such an episode does not occur, then it will be defined as=0 'NO' [Time Frame: Maximum time frame 50 days postoperatively]
- Disease recurrence. Disease recurrence rate. If such an episode occurs, then it will be defined as=1 'YES' If such an episode does not occur, then it will be defined as=0 'NO' [Time Frame: Maximum time frame 1 year postoperatively]
- Difference in the quality of life of the patient. Difference in the quality of life of the patient based on the Quality of Life with Chronic Wounds Wounds (Qol) Questionnaire [Time Frame: 7, 14 and 21 days postoperatively]

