## **8. Experimental Group**

The pilonidal cyst will be resected, with the use of a scalpel and then hemostasis will be performed with diathermy.

Alginate dressings with silver and high-G cellulose, which combine increased absorption properties, antimicrobial action and high coherence will be used. The size of the dressings will be 3cm X 45cm and 1 cm cord will be used for filling the wound cavity. Dressings with perimetric adhesive layer from natural materials for latent breathing of the skin with dressing dimensions based on the wound size, will be also placed.

Wound care will be performed in a specific way each time that the dressings will be removed. The wound will be irrigated with normal saline and betadine solution and finally without pressure the trauma will be dried.

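### The allocation is disclosed before the excision although the arms differ only in the dressing that follows, so the surgeon may know the arm while making the wound whose healing time is the primary endpoint.

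*Protocol*

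**What the plan says.** Section 5 (Randomization) provides for "an opaque envelope, which will contain the allocation group for the specific patient", and this envelope "will be opened preoperatively upon the entry of the patient into the surgical room". It does not say who opens it or who learns the result.

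Section 6 (Blinding) masks only the investigator who records postoperative data and adds: "There will be no blinding at the level of the surgeon or the patient".

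Section 8 (Experimental Group) begins with the operation: "The pilonidal cyst will be resected, with the use of a scalpel and then hemostasis will be performed with diathermy". Section 9 (Active Comparator) repeats that sentence word for word. Only then do the arms part: silver alginate filling with an adhesive cover in one, simple gauze in the other. Irrigation and drying at later dressing changes are again the same.

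The primary endpoint in section 7 is "Postoperative required time for wound healing. Measurement unit: days. [Time Frame: Maximum time frame 50 days postoperatively". The secondary endpoints include "Disease recurrence. Disease recurrence rate" and "Wound hematoma. Hematoma of the wound".

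The Introduction says that chronic disease is best treated by "complete resection of the cyst along with the coexisting fistulas, in order to ensure the minimum reoccurrence rate". That is background. The methods fix no excision margin and do not ask for the cavity to be measured.

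**The concern.** The operation creates the wound whose healing is then timed. If the surgeon knows the arm while cutting, the extent of the excision could differ between arms. Cavity size, and with it healing time, could then differ for a reason other than the dressing. The same steps bear on two secondary endpoints: the Introduction ties complete resection to low recurrence, and haemostasis plausibly bears on haematoma.

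The existing safeguards do not cover this interval. The opaque envelope protects concealment up to entry into the room, and this is not a failure of enrolment concealment. The masked recorder works after the operation and would faithfully record any difference made during it. With no cavity measurement planned, such a difference could be neither seen nor adjusted for.

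**Working it through.** **Order of events**

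| Step | Experimental arm (section 8) | Comparator (section 9) | Allocation needed? |
|---|---|---|---|
| Entry to surgical room | envelope opened (section 5) | envelope opened (section 5) | no |
| Resection | scalpel | scalpel, same sentence | no |
| Haemostasis | diathermy | diathermy, same sentence | no |
| First dressing | silver alginate and adhesive cover | simple gauze | yes |

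The gap runs from entry to the room until the first dressing. The protocol gives no reason for disclosing the arm before the last row.

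**Inputs** (section 1, sample size): mean healing time 60.4 days, SD 6.2, target reduction 5%, alpha 0.05, power 90%, 89 per arm. Section 7 gives the 50-day limit. The documents give no figure for a shift caused by the excision, so the shifts of 0.25, 0.5 and 1 day are assumptions.

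**The plan's own figure.** Target difference = 0.05 × 60.4 = 3.02 days. With a two-sided test (sidedness is not stated, but one-sided gives 73), n = 2 × (1.960 + 1.282)² × 6.2² / 3.02² = 88.6, so 89 per arm. This reproduces the protocol. Power at 89 is 90.1% by the normal formula and 89.8% by the t-test. The timing of disclosure does not affect it.

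**No limit at 50 days.** Standard error of the difference = 6.2 × √(2/89) = 0.929 days. A shift b with no dressing effect gives a noncentral t with 176 degrees of freedom and noncentrality b/0.929.

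| Shift b (assumed) | b/0.929 | Two-sided rejection rate |
|---|---|---|
| 0 | 0 | 5.0% |
| 0.25 day | 0.27 | 5.8% |
| 0.5 day | 0.54 | 8.3% |
| 1 day | 1.08 | 18.8% |

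If a 1-day shift ran against the experimental arm, a true 3.02-day benefit would appear as 2.02 days, and power would fall from 90% to 58%.

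**With the 50-day limit.** These figures do not carry over directly. With normal healing times at the protocol's mean, the share of controls healed by day 50 is Φ((50 − 60.4)/6.2) = Φ(−1.68) = 4.7%. At the target mean of 57.38 it is Φ(−1.19) = 11.7%. The table gives rejection rates for a log-rank test censored at day 50, with 20,000 simulated trials per cell. Simulation error near 5% is about √(0.05 × 0.95/20,000) = 0.15 percentage points.

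| Control mean | No shift | 0.25 day | 0.5 day | 1 day |
|---|---|---|---|---|
| 60.4 days (protocol) | 4.3% | 4.6% | 5.1% | 7.6% |
| 50 days (assumed) | 5.0% | 5.6% | 7.5% | 15.2% |
| 40 days (assumed) | 5.3% | 6.0% | 8.0% | 16.6% |

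For a 1-day shift the range is thus about 8% to 19%, depending on how far the limit binds.

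**The case against.** The strongest reply is that this is an opportunity for bias and not an error. No two sections conflict, and no figure is wrong. Section 5 does not say that the surgeon sees the envelope, and section 6 would need an unblinded surgeon anyway once dressings go on. Both arms prescribe the same resection, disease extent largely drives the cavity, and it is not obvious why knowing the dressing would make a surgeon cut more or less. Every shift is assumed, and 1 day is a third of the whole target effect (1/3.02). On the protocol's own mean with the 50-day limit, shifts of 0.25 and 0.5 day leave the error rate close to nominal. Under that limit, power for 3.02 days is only about 41% before any excision bias, so the limit matters far more than the envelope. Finally, surgeon and patient stay unblinded through the weeks of wound care.

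Much of this stands. The mechanism is plausible but unproven, its direction is unknown, the uncapped figures do not describe the endpoint as written, and the gain is confined to the operation.

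It does not remove the point. That the surgeon must know the arm once the dressing is applied is no reason to disclose it before the incision. Where a protocol neither withholds the result nor measures the cavity, it cannot later show that the excision was independent of the arm. Nor can an analysis plan restore masking, and adjustment needs a measurement that the protocol does not plan.

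**Conclusion.** The concern holds. The protocol discloses the arm earlier than its own procedures require, and so leaves an avoidable route by which knowledge of the arm could affect the excision and haemostasis. The order of events rests on the text alone. That the surgeon learns the result when the envelope is opened is an inference: the protocol does not state it, and does not prevent it.

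The size of any bias cannot be derived from the documents. The illustrations assume a systematic shift, normal healing times with SD 6.2, 89 per arm, and a t-test or a log-rank test censored at day 50. On those assumptions a 1-day shift is material, and shifts of half a day or less range from negligible to modest. The point does not invalidate the trial, but the change should be made because the remedy is simple.

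**What to change.** Amend section 5 to read, in substance: *The opaque envelope is opened in the operating room once resection and haemostasis are complete and the cavity dimensions have been recorded, immediately before the first dressing is placed.* The recorded size then precedes disclosure in every patient and can serve as a covariate for healing time.

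If the timing cannot be changed, record the cavity dimensions before the first dressing in both arms and adjust for them. This is only a partial repair, because other aspects of the operation, such as diathermy use, would stay unmeasured.

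The cost is small but not nil: both dressing sets must be at hand at each operation, and one brief measurement is added. The sample size is unaffected. The benefit is limited to the operative step, since surgeon and patient remain unblinded afterwards.

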## 6. Blinding

Blinding will exist at the level of the investigator who will record the data postoperatively. There will be no blinding at the level of the surgeon or the patient.

## 7. Endpoints

### *Primary Outcome Measure:*

- Wound healing time. Postoperative required time for wound healing. Measurement unit: days. [Time Frame: Maximum time frame 50 days postoperatively]

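### The primary endpoint stops at day 50, but the sample size assumes healing at 60.4 ± 6.2 days: about 90% of wounds would still be open and power is about 30–50%, not 90%

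*Protocol*

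**What the plan says.** In Materials and Methods, section 1, on sample size, the Protocol takes its planning value of 60.4 ± 6.2 days from a cited study and introduces it with the words "According to literature, the mean time required for wound healing of patients subjected to pilonidal cyst resection is". The target is healing that is 5% shorter, with equal allocation to the two arms. The section concludes as follows: "with alpha 0,05 and 90% power, the required number of patients in each group is 89". It also excludes and replaces patients who do not complete follow-up.

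Section 7 of the Protocol, on endpoints, names one primary outcome and describes it in this way: "Wound healing time. Postoperative required time for wound healing. Measurement unit: days. [Time Frame: Maximum time frame 50 days postoperatively".

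Among the secondary outcomes, return to everyday activities and dressing cost have the same limit, for example "Cost of the material. Overall cost of the dressings applied [Time Frame: Maximum time frame 50 days postoperatively". The weekly assessments end at day 49. Only recurrence is followed longer, to 1 year. Nothing in the Protocol extends the observation of healing past day 50.

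**The concern.** The two sections describe the same variable and cannot both hold. One says the average wound takes about 60 days to close. The other stops looking at day 50. The sample size treats each healing time as a measured number, whereas the endpoint as defined would leave most patients without one.

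At stake is the primary comparison itself, because nearly all of the 3-day benefit the trial is sized to detect would occur after the window closes. If open wounds are entered as 50 days, the two means become almost equal. If only healed wounds are averaged, the comparison is between two small groups selected for fast healing. If open wounds are censored, the test rests on about 14 events among 178 patients. In each case a true 5% benefit is more likely to be missed than found.

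**Working it through.** **Inputs.** From section 1: control mean 60.4 days, SD 6.2, reduction 5%, alpha 0.05, power 90%, 1:1 allocation, 89 per arm. From section 7: window of 50 days. Assumptions: the ± value is an SD, the test is two-sided, healing times are roughly normal, and healing is not recorded after day 50.

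**1. Reproducing the plan's figure.**
- Difference: 0.05 × 60.4 = 3.02 days, so the experimental mean is 60.4 − 3.02 = 57.38 days.
- n per arm = 2 × (1.960 + 1.282)² × 6.2² / 3.02² = 88.6, rounded up to 89. Power at 89 is 90.1%.
- A one-sided test would give 73. The plan's figure is therefore the two-sided one, with ± read as an SD and all times observed.

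**2. Share healed by day 50**, Φ((50 − mean)/6.2):
- Control: (50 − 60.4)/6.2 = −1.68; Φ = 0.047; 0.047 × 89 ≈ 4 patients.
- Experimental: (50 − 57.38)/6.2 = −1.19; Φ = 0.117; 0.117 × 89 ≈ 10 patients.
- Still open: 95.3% and 88.3%, or 91.8% over both arms.

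**3. Mean difference when times are cut at day 50.** The expected capped time is 50 − 6.2 × [zΦ(z) + φ(z)], where z is the standardised value from step 2.
- Control: 50 − 0.12 = 49.88 days.
- Experimental: 50 − 0.35 = 49.65 days.
- Difference: 0.23 days, against 3.02 uncapped. Among healed patients only, the simulated difference is about 0.45 days.

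**4. Power with 89 per arm and the day-50 limit** (4,000 to 10,000 simulated trials; the two-proportions figure is by formula):

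| Analysis | Power |
|---|---|
| t-test, all times observed | 90% |
| Log-rank, open wounds censored at day 50 | about 40% |
| Rank-sum on capped times | 40% |
| Two proportions healed by day 50 (normal approximation) | 40% |
| Fisher exact on the same proportions | 32% |
| t-test on capped times | 31% |
| t-test in healed patients only | 4% |

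With lognormal times of the same mean and SD, the t-test on capped times gives 40% and the log-rank test 49%.

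**5. What the 50-day window would need.** About 319 per arm for the two proportions. For the log-rank test, 275 per arm gives 87% and 325 gives 92%.

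**6. A longer window.** At day 75, 99.1% of control wounds have healed; at day 80, 99.9%. Simulated t-test power is about 90% at either limit. Log-rank power is about 84%.

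**7. If the planning mean is the wrong figure.** For about 95% of controls to heal by day 50 with SD 6.2, the mean must be near 50 − 1.645 × 6.2 = 39.8, say 40 days. Five per cent of that is 2.0 days. With SD 6.2, power at 89 per arm is about 58%. If the SD instead scales with the mean (6.2/60.4 × 40 = 4.1 days), the standardised effect is unchanged and power stays at about 90%.

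**The case against.** The strongest reply is that the planning mean, not the window, may be the error. Weekly visits end at day 49, overall satisfaction is rated at day 50, and satisfaction with the treatment results is rated at day 35. That schedule suits a sponsor who expects closure within about 50 days. On that reading power could still be 90% if the SD falls in proportion to the mean. This stands as a possibility, and the Protocol does not show which section is wrong. It does not remove the conflict, because the stated power would then rest on a healing time the sponsor does not expect.

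A second reply is that the time frame is only a label and that open wounds may be dealt with in the SAP. But it is the Protocol's only statement of how long healing is observed, and it is worded as a maximum. No all-patient analysis tried brings power near 90% at 89 per arm, so the choice of method cannot repair it.

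Two narrower points do stand. The exact loss depends on the shape of the distribution: 31% to 41% with normal times, 40% to 49% with lognormal. And the Protocol gives no expected time to return to everyday activities, so truncation of that outcome is plausible but not shown. The case for dressing cost is stronger, since dressings would continue on open wounds.

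**Conclusion.** The concern holds. The arithmetic behind 89 per arm is correct for fully observed healing times, but the endpoint as defined does not supply them. On the Protocol's own figures about 92% of wounds would be open at the limit. Power would be roughly 30% to 50%, depending on analysis and distribution, so a true 5% benefit would be missed in about half to 70% of such trials. This rests on 60.4 ± 6.2 being a mean and SD that apply to these patients, and on day 50 being the end of healing observation. If either is not intended, the text still has to change, because the planning value or the time frame is then misstated. As this affects the primary endpoint, it should be corrected before the trial relies on the stated power.

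**What to change.** **Preferred:** change the primary time frame from 50 to at least 80 days, with wounds still open then treated as censored. State in section 1 that an open wound at the end of the window is not a failure to complete follow-up, so that slow healers are not excluded and replaced. Extend the dressing-cost window to match, and review the return-to-activities window at the same time.

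The 90% then holds for a comparison of means. If the primary test is a log-rank test, state about 84% or re-derive the sample size for that test.

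**If 50 days must stay:** restate the power for that window (about 30–40% under normal times, up to 49% under lognormal), or re-size the trial at roughly 300 to 325 per arm.

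**If healing within 50 days is expected:** replace the 60.4-day value and its SD with justified figures and re-derive the power. At a mean of 40 days it runs from about 58% (SD 6.2) to about 90% (SD 4.1).

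**Cost of the preferred change:** a short amendment to the time frames and the replacement rule, and about 30 more days of recording wound status by the blinded recorder. Patients are already followed to 1 year for recurrence. No additional patients are needed for the comparison of means.

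### The primary endpoint is raw days to healing of an open cavity, but the protocol does not provide for recording initial cavity size in either arm, which costs precision and removes any check that excision was equal

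*Protocol*

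**What the plan says.** Protocol section 7 (Endpoints) defines the primary outcome as "Wound healing time. Postoperative required time for wound healing. Measurement unit: days", with "Time Frame: Maximum time frame 50 days postoperatively". It is not standardised for the size of the wound.

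Section 3 (Inclusion Criteria) admits "Disease stage I,II,III and IV". Under section 2 (Disease staging system) this runs from "IA Asymptomatic one or more pit(s) on the natal cleft without a history of abscess" to recurrent disease. The stages describe pit position, symptoms and history, not the wound left after excision.

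Wound size appears once, in section 8 (Experimental Group): "dressing dimensions based on the wound size, will be also placed". Section 9 (Active Comparator) does not mention it. No endpoint and neither treatment section calls for cavity length, width, depth, area or volume.

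Section 5 (Randomization) has the envelope opened when the patient enters the operating room, so before excision, and states no stratification. Section 6 (Blinding) leaves the surgeon unblinded. Sections 8 and 9 describe the excision and haemostasis identically.

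**The concern.** An open cavity heals by filling in, so its starting size plausibly influences the number of days to closure. If size is not measured at operation, the value is lost. A statistical analysis plan can choose covariates only from data that were collected, so this is a matter for the protocol.

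Two things are at stake. The first is precision: size-related variation stays in the error term of a comparison whose target difference is only about 3 days. The second is interpretability. The surgeon who creates the cavity already knows which dressing will go into it. If excision extent differed between arms for that reason, healing time would differ for a reason unrelated to the dressing, and no recorded data would show it. Randomisation does not guard against differences that arise after the allocation is disclosed.

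**Working it through.** **Inputs from the protocol (section 1).** Mean 60.4 days, SD 6.2 days, "for a 5% decrease in the duration of the healing process", and "with alpha 0,05 and 90% power, the required number of patients in each group is 89".

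**Assumed input.** The correlation r between initial cavity size and healing time. The documents give none, so 0.3, 0.5 and 0.7 are shown.

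**Step 1: reproduce the plan's figure.** Target difference = 0.05 × 60.4 = 3.02 days. Sidedness is not stated; two-sided 0.05 gives

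n = 2 × (1.960 + 1.282)² × 6.2² / 3.02² = 88.6, so 89 per group.

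Power at 89 per group is 90.1%. The figure reproduces with no covariate, using a total SD.

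**Step 2: planned precision.** Standard error = 6.2 × √(2/89) = 0.93 days. The 95% half-width = 1.96 × 0.93 = 1.82 days.

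**Step 3: precision if size were measured before allocation and adjusted for.** Half-width = 1.96 × 6.2 × √[(2/89)(1 − r²)]. The equivalent gain in sample size is 1/(1 − r²) − 1. The imbalance SD, r × 6.2 × √(2/89), is the spread in the unadjusted difference that comes from chance imbalance in size.

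| Assumed r | Half-width (days) | Equivalent extra patients | Imbalance SD (days) |
|---|---|---|---|
| 0 | 1.82 | 0% | 0 |
| 0.3 | 1.74 | 10% | 0.28 |
| 0.5 | 1.58 | 33% | 0.46 |
| 0.7 | 1.30 | 96% | 0.65 |

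**Step 4: is the imbalance an extra error?** No. At r = 0.5 the variance of the difference splits into 0.46² + 0.80² ≈ 0.86 (0.80 = 1.58/1.96), which is the 0.93² already used in Step 2. The imbalance column is a component of the planned standard error, not an addition to it.

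**Step 5: limit on these figures.** They treat every healing time as observed. With the protocol's mean and SD, and normality assumed, the share healed by day 50 is Φ((50 − 60.4)/6.2) = 4.7% in the control arm. At the target mean of 57.38 days it is Φ((50 − 57.38)/6.2) = 11.7%. If observation really stops at day 50, the half-widths above do not describe the endpoint.

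**Step 6: order of events.** As written, the sequence is envelope opened, cavity excised by an unblinded surgeon, dressing placed. A size measured in that sequence is a post-allocation variable. Because the excision is described identically in both arms, the surgeon does not need the allocation until a dressing has to be chosen.

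**The case against.** The strongest case on the other side is that nothing in the stated plan is broken. The SD of 6.2 is unadjusted, the sample size reproduces without a covariate, and 1.82 days is the precision that was planned. Under 1:1 randomisation the confidence interval already allows for chance imbalance in cavity size. All of this stands, and it limits the precision part of the point to a missed gain, small at r = 0.3.

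A reader might infer more: that cavity size is the main determinant of healing time, that imbalance cannot be corrected, or that the trial is underpowered. The documents support none of these.

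- No section says what determines healing time, and the correlations here are assumptions.
- Stage is assigned to every patient and allows partial adjustment.
- Power would fall only if these patients vary more than the cited SD (an assumed SD of 8 would give 71%), and no figure in the protocol shows that they do.
- Since stage does not measure the wound, the range of stages is only weak evidence of a range of cavity sizes.

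It may also be said that size could be noted informally. Section 12 (Trial) sends patient data to charts and a database, and the protocol has no baseline data list. The claim is therefore that the protocol does not provide for recording size, not that it will go unrecorded. Naming covariates can be left to the analysis plan; taking the measurement cannot.

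The last objection is that simply adding a measurement would not give a clean baseline covariate, because the allocation is already known. That is correct, and the fix has to deal with it.

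**Conclusion.** The point holds as a worthwhile and cheap improvement to the design, not as an error that invalidates the comparison. The 89 per group and 90% power are unaffected. What is lost is precision, between 0.08 days of half-width (1.82 to 1.74) at r = 0.3 and 0.52 days (1.82 to 1.30) at r = 0.7, against a 3.02-day target. These sizes rest on the assumed correlations, on SD 6.2 applying to this population, and on healing times being fully observed despite the 50-day limit.

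Also lost is the only direct check that excision extent was equal between arms. No size can be put on that from the documents. Unlike chance imbalance, a systematic difference of this kind would not be covered by the confidence interval.

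**What to change.** 1. In sections 8 and 9, in identical words: after haemostasis and before any dressing is placed, measure cavity length, width and depth with a sterile ruler and record them for every patient.
2. In section 5: open the envelope only after that measurement is recorded. Size then becomes a true baseline value, and the excision is made without knowledge of the allocation.
3. Use initial cavity size, with the recorded disease stage, as baseline covariates for healing time. This sentence may sit in the analysis plan.

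If the present envelope timing is kept, still take the measurement and report cavity size by arm. Adjust the primary analysis for preoperative stage only, and treat the size-adjusted result as supportive, because size would then be a post-allocation variable and adjusting for it could introduce bias.

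The cost is about a minute per operation, three data fields, and an envelope opened during the operation instead of at entry to the room. No additional patients are needed.
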